10.3 POPULATIONS FOR ANALYSES

The analysis population will include all enrolled participants who received at least 1 dose of study medication (mycophenolate mofetil or placebo) during treatment period (modified intention to treat, mITT). The protocol

population will be all participants who attend all study visits and complete the trial.

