5 STUDY DESIGN

5.1 OVERALL DESIGN

Hypothesis: MMF for 12 weeks can safely attenuate immunogenicity conferred by pegloticase as determined by the proportion of participants achieving and maintaining an sUA ≤ to 6 mg/dL through 12 weeks, compared to concurrent controls

Phase of trial: Phase II

Design of trial: Randomized, double-blind, placebo controlled

Single or multi-site: Multisite (UAB, University of Michigan[UM], and up to 6 to be named sites)

Number of Arms: Two arms; Intervention Arm: pegloticase + MMF (peg + MMF); Placebo Comparator Arm: pegloticase

+ placebo (peg + PBO)

Methods to minimize bias: Participants will be randomized 3:1 to either peg+MMF or to peg+PBO. Randomization allocation will be balanced by site to achieve 24 peg+MMF and 8 peg+PBO using the double-blind design

During the first 12 weeks, participants randomized to the peg+MMF arm will receive a combination of pegloticase and MMF. Patients experience reduced immunogenicity when a loading dose of anti-proliferative agent is administered *prior* to a monoclonal antibody in other disease states, ²⁷⁻³⁰ thus, for those randomized to the peg+MMF arm we will begin a MMF run-in at 500 mg/twice per day for the first week, and if tolerated titrate the dose up to 1000mg/twice per day for the second week of run-in prior to initial pegloticase infusion. MMF (or matching PBO in the other arm) will be titrated to 1000 mg/twice per day (a standard, well-tolerated dose used in other rheumatic diseases)⁶ concurrent with the first pegloticase infusion. Next, a total of up to 12 infusions of pegloticase 8 mg IV will be administered on a biweekly basis. To understand the long-term efficacy (durability) and safety of this approach, and to minimize the exposure to MMF, following the first 12 weeks of dual therapy phase, all participants will be given an additional three months of open-label pegloticase only therapy (see **Figure 1**) and will be followed.

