5.3 JUSTIFICATION FOR DOSE

For those randomized to the peg+MMF arm we will begin a MMF run-in at 500 mg/twice per day for the first week, and if tolerated titrate the dose up to 1000mg/twice per day for the second week of run-in prior to initial pegloticase infusion. MMF (or matching PBO in the other arm) will be titrated to 1000 mg/twice per day, the standard, well-tolerated dose used in other rheumatic diseases⁶ (concurrent with the first pegloticase infusion).

All participants in the study will receive pegloticase at the FDA approved dose of 8 mg administered intravenously every 2 weeks for a total of 6 infusions over a 12-week treatment period, and over an additional 12-week pegloticase opt-in follow-up period (per standard of care).

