7.1 STUDY INTERVENTION(S) ADMINISTRATION

7.1.1 STUDY INTERVENTION DESCRIPTION OVERVIEW

Participants will be randomized 3:1 to either pegloticase + MMF (Peg+MMF) or to pegloticase + placebo (peg+PBO).

Experimental Arm:

Participants randomized to this arm will receive pegloticase + mycophenolate mofetil.

Drug: Mycophenolate Mofetil

Participants randomized to the pegloticase + MMF arm will start on 1) Pegloticase 8 mg intravenously (IV) every two weeks, and 2) mycophenolate mofetil at 500 mg/BID and titrating up to 1000 mg/BID in 2 weeks if tolerated. Mycophenolate mofetil therapy will continue for 12 weeks at the highest tolerated dose. After the 12-week combination mycophenolate mofetil and pegloticase study period, participants will continue open-label pegloticase therapy for an additional three months.

Drug: Pegloticase 8 mg/mL [Krystexxa]

Participants randomized to the pegloticase + MMF arm will start on 1) Pegloticase 8 mg IV every two weeks#, and 2) mycophenolate mofetil at 500 mg/BID and titrating up to 1000 mg/BID in 2 weeks if tolerated. Mycophenolate mofetil therapy will continue for 12 weeks at the highest tolerated dose. After the 12-week combination mycophenolate mofetil and pegloticase study period, participants will continue open label pegloticase therapy for an additional three months. Other Name: Krystexxa

Placebo Comparator Arm:

Participants randomized to this arm will receive pegloticase + placebo

Drug: Placebo

Participants randomized to the pegloticase + placebo will receive placebo instead of mycophenolate mofetil therapy for 12 weeks. After the 12-week combination placebo and pegloticase study period, participants will continue open label pegloticase therapy for an additional three months.

Drug: Pegloticase 8 MG/ML [Krystexxa]

Participants randomized to the pegloticase + placebo will receive placebo instead of Mycophenolate mofetil therapy for 12 weeks. After the 12-week combination placebo and pegloticase study period, participants will continue open label pegloticase therapy for an additional three months.

Other Name: Krystexxa

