9 STUDY ASSESSMENTS AND PROCEDURES

This study will be coordinated by the University of Alabama at Birmingham (UAB). All study visits and procedures will be performed at the United States, at UAB, the University of Michigan, and up to 6 to be named sites. Enrollment will be competitive between sites. Frequency of study visits and clinical evaluations can be found in **Table 1**. Following the first 12 week dual therapy phase, participants will be given an additional three months of open-label pegloticase only therapy (see **Figure 1**) and will be followed to better understand the long-term efficacy (durability) of this approach, which is essential for future studies. Specifically, we will whether assess the durability of the short course of MMF continues over the next 12 weeks in the absence of MMF.

Participants will be seen according to schedule of visits and evaluations outlined in **Table 1** and per the details that follow:

Visit 1 - Screening Visit

The screening visit will take approximately 1 hour to complete. Potential participants will be screened to determine if they satisfy all inclusion and exclusion criteria. Men and women 18 years of age or older will be invited to proceed with informed consent (IC) and enroll in the study. At the screening visit, the study objectives will be explained to potential participants. After all questions raised by a potential participant are answered, and before any protocol-specified screening procedures are initiated, they will be offered the IC for the screening evaluation. A copy of the signed and dated IC form must be provided to the participant. After IC is obtained, a participant number will be assigned. All screening procedures must be completed and eligibility criteria met prior to start of immune-modulating therapy and pegloticase infusions. Basic demographic information and reason(s) for exclusion must be completed on the specified case report form (eCRF) pages for all participants who signed an ICF, but never received pegloticase. During the screening visit, the following procedures will be performed, and information will be obtained to determine eligibility to continue in this research study:

- o Review inclusion/exclusion criteria
- o ICF
- o Date of birth
- Self-reported race/ethnicity
- Medical history that might preclude study participation
- Gout history and symptom severity
- Medication review

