All women of childbearing potential must use an effective form of birth control during this study and for 30 days after completion of the study. Acceptable methods of birth control include hormonal control methods, inter-uterine device, a double-barrier method (diaphragm with spermicide, condom with spermicide) or abstinence. All male participants will be cautioned to use proper birth control methods with their partners during the course of the study in which MMF is received.³

Laboratory: sUA, CMP, CBC with diff, and pregnancy test for premenopausal women. Additionally, a sample will be collected at screening, Visits 1, 8, 11, 14, and 17-20 for evaluation of anti-pegloticase Ab. Serum samples (see **Appendix 5)** will be collected and prepared for transport to the clinical research lab in the Division of Clinical Immunology and

Rheumatology at the University of Alabama at Birmingham. All lab samples will be discarded if the participant is deemed not eligible for the study.

Visit 2 - Run-In Visit

- Obtain and record vital signs, including pulse rate, sitting blood pressure, and body temperature
- Review / update concomitant medications
- Gout Flare/tophus assessment
- o Blood draw
- Laboratory
 - sUA
 - Urine pregnancy test for premenopausal women
 - CMP
- Randomization will occur at Visit 2/Run-In. Dispense 2 week course of MMF (500mg/twice per day for the first week, and 1000mg/twice per day for the second week of run-in) or placebo, with dosing instructions per randomization assignment.
- Gout Flare Prophylaxis

Participants will be placed on a prophylactic regimen of colchicine or NSAID to prevent gout flares, unless medically contraindicated or not tolerated, and will receive this prophylaxis for at least two weeks prior to the first administration of pegloticase. Gout flare prophylaxis will continue for the duration of the study unless medically contraindicated or not tolerated.

Visit 3 (Baseline-0 weeks)

Visit 3 will occur within 2 weeks of the run-in visit.

The markers for the study primary and secondary outcomes will be collected at each visit. Other data will be collected as needed for safety monitoring.

- Obtain and record vital signs, including pulse rate, sitting blood pressure, and body temperature
- Review / update concomitant medications
- Assess any AEs, and record
- Gout Flare assessment
- Assess compliance (via pill count) and dispense course of MMF (1000 mg/twice per day) or PBO, with dosing instructions

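### The mITT definition in 10.3 depends on an undefined treatment period; on the protocol's own usage it can exclude randomised participants who took MMF or placebo only in the run-in.

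*Combined protocol and SAP*

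**What the plan says.** - **Analysis set (10.3).** The population is enrolled participants "who received at least 1 dose of study medication (mycophenolate mofetil or placebo) during treatment period (modified intention to treat, mITT"). The period is not defined there. The only other set is a per-protocol-type set of those who attend every visit and complete the trial. No set of all randomised participants is defined.
- **Other uses of the term.** Section 5.3 describes pegloticase as given "every 2 weeks for a total of 6 infusions over a 12-week treatment period", and 7.2.2 uses the same phrase. These are the only other places where it occurs.
- **Randomisation and first dose (section 9, Visit 2, week -2).** "Randomization will occur at Visit 2/Run-In", and the visit instruction continues: "Dispense 2 week course of MMF (500mg/twice per day for the first week, and 1000mg/twice per day for the second week of run-in) or placebo". Table 1 puts Visit 2 under Screen/Run-In, apart from Phase 1.
- **Combination phase (5.1).** "During the first 12 weeks, participants randomized to the peg+MMF arm will receive a combination of pegloticase and MMF".
- **A description that points the other way (7.1.1).** The titration is set out as part of the MMF intervention, followed by: "Mycophenolate mofetil therapy will continue for 12 weeks at the highest tolerated dose".
- **Record for the never-infused (section 9, Visit 1).** Demographics and reasons for exclusion must be completed "for all participants who signed an ICF, but never received pegloticase".
- **Scoring (10.4.1).** Participants who do not tolerate MMF, withdraw or are not evaluable before Week 12 count as failures, but the sentence places this in sensitivity analyses. Section 10.4.7 separately provides for imputation of missing outcomes.

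**The concern.** The condition for entering the mITT is a dose of blinded drug inside a period that the plan does not delimit. If the period starts at Week 0, as the wording of 5.3 and 7.2.2 suggests, a participant randomised at Visit 2 who takes run-in doses and none afterwards does not meet it. That removal happens after randomisation. It is plausibly related to treatment, because MMF is the active drug in the run-in and 3.3.1 lists nausea (20%) and persistent diarrhea (36%) among its immediate risks. The amendment history gives earlier detection of MMF intolerance as a reason for the run-in titration, so this is where early stopping would be expected to show.

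At stake is the comparison that feeds Figure 4. If MMF-intolerant participants are dropped from the MMF arm only, the comparison estimates response among those who could take MMF, not among those assigned to it. Two statisticians could build different primary sets from the same text, and there is no as-randomised set to fall back on.

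**Working it through.** **1. The plan's own figures reproduce.** Section 10.2 gives 82 per group for 60% vs 80%, 80% power, two-sided 5%. With pooled variance and no continuity correction:

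n = [1.960·√(2·0.7·0.3) + 0.842·√(0.6·0.4 + 0.8·0.2)]² / 0.2² = 81.2, which rounds up to 82.

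Readable Figure 4 entries also match two-sided Fisher tests at 24 vs 8. With 5 control successes, 20, 21 and 22 MMF successes give 0.33, 0.15 and 0.09; 20 MMF against 3 control successes gives 0.02. So the green rule (10.4.1) is a two-sided Fisher p < 0.10 in favour of MMF.

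**2. Two readings of 10.3.**

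| Start of the period | Support | Participant dosed only in the run-in |
|---|---|---|
| Week 0 | 5.3 and 7.2.2 (12 weeks, six infusions); Table 1 separates the run-in from Phase 1 | Not in the mITT |
| Visit 2 | 10.3 refers to MMF/placebo doses, which start at Visit 2; 7.1.1 includes the titration in the intervention | In the mITT |

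On the second reading the qualifier adds almost nothing to the one-dose condition, because MMF/placebo is first dispensed at Visit 2. That favours the first reading but does not settle it.

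**3. Can one or two participants change the colour?** Stoppers have no success, so keeping them leaves the MMF denominator at 24, and excluding k of them makes it 24 − k. Two-sided Fisher p:

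| Stoppers (MMF) | Kept | Excluded |
|---|---|---|
| 1 | 20/24 vs 4/8: 0.152 | 20/23 vs 4/8: 0.053 |
| 1 | 17/24 vs 3/8: 0.116 | 17/23 vs 3/8: 0.095 |
| 2 | 19/24 vs 4/8: 0.176 | 19/22 vs 4/8: 0.060 |

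Each pair moves from yellow to green. Figure 4 itself is tabulated only for 24 vs 8, so the excluded column applies the same rule outside the table.

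**4. Chance of a green result.** Inputs from 10.2 and 10.4.1: 60% control success, 80% MMF success (applied here to those who do not stop), 24 vs 8. Assumed, because the documents give no run-in stopping rate: k = 1, 2 or 3 MMF stoppers and j = 0 or 1 placebo stopper, with no replacements.

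P(green) = Σ Bin(a; 24 − k, 0.8) · Bin(b; 8 − j, 0.6), summed over pairs (a, b) where MMF has the higher proportion and p < 0.10. The Fisher test uses denominators 24 − k and 8 − j if stoppers are excluded, and 24 and 8 if they are kept as failures.

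| MMF stoppers | Placebo stoppers | Excluded | Kept as failures |
|---|---|---|---|
| 0 | 0 | 24.3% | 24.3% |
| 1 | 0 | 26.0% | 17.5% |
| 2 | 0 | 23.0% | 12.5% |
| 3 | 0 | 24.7% | 8.8% |
| 1 | 1 | 22.8% | 27.4% |
| 2 | 1 | 24.4% | 20.7% |
| 3 | 1 | 21.4% | 15.3% |

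The expected MMF success rate is 80% if stoppers are excluded. If they are kept as failures it is 0.8·(24 − k)/24, that is 76.7%, 73.3% and 70.0% for k = 1, 2, 3.

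**The case against.** The strongest answer is that no passage states the exclusion. The condition in 10.3 is about MMF/placebo, so its treatment period can naturally be that drug's dosing period. Sections 5.3 and 7.2.2 count infusions of a different drug and do not define a trial-wide term. Section 10.4.1 counts MMF-intolerant participants as failures without setting the run-in apart, and 8.1 keeps those who stop study drug in follow-up. This stands as far as it goes: the exclusion is one reading. But 10.4.1 confines that scoring to sensitivity analyses, and follow-up does not determine membership of the primary set.

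A reader might also infer that the Visit 1 text treats never-infused participants as screen failures. It does not. It sets a minimum record, does not say that only those items are kept, and defines no analysis set. Section 6.4 defines screen failures as people not randomised or not entered.

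The arithmetic has limits too. The excluded figures scatter around the 24.3% obtained with no stoppers, so the contrast comes almost wholly from scoring stoppers as failures, which a change of membership alone would not set. The 20% and 36% in 3.3.1 are event rates, not stopping rates. Because MMF may continue at a tolerated dose, intolerance in the run-in need not mean no dose from Week 0. Replacements under 8.2 and 8.3 are not modelled. Finally, 10.4.3 calls the analyses descriptive, and 10.4.2 makes a green recommendation depend also on safety and an antibody effect, so the Fisher result alone does not decide. These points limit the size of the concern. They do not remove the ambiguity about who is analysed.

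**Conclusion.** The point holds as an ambiguity that should be closed. Section 10.3 does not define its treatment period, and read in line with 5.3 and 7.2.2 it can remove randomised participants dosed only in the run-in, for reasons plausibly linked to MMF.

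The documents do not support saying that such participants are definitely excluded, or that excluding them always favours MMF. With no placebo stoppers, exclusion raises the chance of green by 8.5, 10.5 and 15.9 percentage points for 1, 2 and 3 MMF stoppers, relative to keeping them as failures. With one placebo stopper, the difference is −4.6, +3.7 and +6.1 points. Size and direction therefore rest on assumed stopping counts, on the 80% and 60% success rates, and on failure scoring. What does not rest on assumed rates is that, at 24 vs 8, the handling of a single participant can move a result across the 0.10 line.

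**What to change.** 1. **10.3:** replace the treatment-period qualifier with *at any time from Visit 2 (run-in included)*, so that the mITT is all randomised participants with at least one dose of MMF/placebo, analysed as randomised.
2. **10.4.1:** state that mITT members who stop before Week 12, including in the run-in, count as failures in the primary Fisher test and not only in sensitivity analyses. Without this, the first change settles membership but not scoring.
3. **Section 9, Visit 1:** state that completing the exclusion record does not remove a randomised participant from the mITT. Keep the record of the reason.

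The cost is a phrase or a sentence in each of three places, with no new visits, data or sample size. The downside is that the MMF success rate may read slightly lower.

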8 STUDY INTERVENTION DISCONTINUATION AND PARTICIPANT DISCONTINUATION/WITHDRAWAL

8.1 DISCONTINUATION OF STUDY INTERVENTION

Due to the risk of anaphylaxis and IRs being higher in patients who have lost therapeutic response, participants with two consecutive serum urate levels above 6 mg/dL shall be classified as a non-responder and discontinued from the study. Investigators will obtain a pre-dose serum urate sample for all patients and review results to verify the serum urate level is \leq 6 mg/dL prior to infusion.

Discontinuation from the study intervention does not mean discontinuation from the study, and remaining study

procedures should be completed as indicated by the study protocol. If a clinically significant finding is identified (including, but not limited to changes from baseline) after enrollment, the investigator or qualified designee will determine if any change in participant management is needed. Any new clinically relevant finding will be reported as an adverse event (AE).

The data to be collected at the time of study intervention discontinuation will include the following: If the study drug is discontinued, unless the subject withdraws consent, the participant will complete visit 17 (two weeks post discontinuation) and visits 17-20. If the participant doesn't want to continue with the follow-up visit schedule detailed above, then it is important to complete a close-out visit.

Based on the known safety profiles of pegloticase and MMF and the procedures we have in place, we believe it is very unlikely, but possible that we could witness one serious AE related to infection. We will institute a stopping rule for safety re-evaluation that would occur if we register more than one such serious adverse reaction (eg. infection that leads to hospitalization). We would then stop the study to comprehensively review safety and our study protocols in conjunction with the DSMB. Other serious adverse reaction or deaths may or may not be related to the study and stopping or discontinuation of the study will be considered on an individual basis. See **Appendix 9** Data Safety Monitoring Plan.

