- Assess any AEs, and record
- Gout Flare assessment
- Laboratory Assessments
 - CBC with diff
 - sUA
 - Pregnancy test for premenopausal women
 - CMP
- Gout Flare Prophylaxis
- IR Prophylaxis /Assess for IRs
- o Administer pegloticase infusion, per site guidelines.

Visit 17 (24 weeks)

Participants will complete a final physical exam and update their medical history since enrollment.

- Obtain and record vital signs, including pulse rate, blood pressure, and body temperature
- Review concomitant medications, and record
- Assess any AEs, and record
- o PROs (PROMIS-29 & GIS instrument)
- Physical exam
 - HEENT, and Neck
 - Cardiovascular
 - Respiratory
 - Gastrointestinal
 - Musculoskeletal
 - Neurologic
 - Integumentary
 - VS/Measurements
- Laboratory Assessments
 - CBC with diff
 - sUA
 - Pregnancy test for premenopausal women
 - CMP
 - Pegloticase Antibody/Mechanistic Study

Following completion of Visit 17 participants will continue for an additional 12 weeks without pegloticase infusions for anti-pegloticase antibody testing. In Phase 3, participants will continue with blood draws and banking of biospecimen every 4 weeks.

Reminder: if a participant is discontinued from the study, they will move into long-term follow-up and will be asked to complete visits 17, in addition to the three 1-month visits 18-20.

Visit 18 (28 weeks)

Participants will report 4 weeks following completion of Visit 17 for a blood draw and banking of biospecimen for antipegloticase antibody testing.

Assessments

- Adverse events
- Pegloticase Antibody/Mechanistic Study

Visit 19 (32 weeks)

Participants will report 4 weeks following completion of Visit 18 for a blood draw and banking of biospecimen for antipegloticase antibody testing.

Assessments

- Adverse events
- Pegloticase Antibody/Mechanistic Study

Visit 20 (36 weeks-Final/visit)

Participants will report 4 weeks following completion of Visit 19 for a blood draw and banking of biospecimen for antipegloticase antibody testing.

Assessments

Adverse events

Pegloticase Antibody/Mechanistic Study

Unscheduled Visit

An unscheduled Visit will be conducted in the event of a suspected AE thought to be serious.

- Obtain and record vital signs, including pulse rate, blood pressure, and body temperature
- Review concomitant medications, and record
- Assess any AEs, and record
- Physical exam includes, but is not limited to
 - HEENT, and Neck
 - Cardiovascular
 - Respiratory
 - Gastrointestinal
 - Musculoskeletal

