 - Neurologic
 - Integumentary
 - VS/Measurements
- Laboratory Assessments
 - CBC with diff
 - IgG
 - sUA
 - CMP
 - Pegloticase Antibody/Mechanistic Study

Follow-up

We will follow each participant from screening for up to six months until completion of the full study (week 36). If the study drug is discontinued, unless the subject withdraws consent, the subject will be followed for the full study period and all data will be collected as scheduled.

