One of the primary objectives of this feasibility pilot study is to determine if there is an overall reduction in immunogenicity leading to increased responders to pegloticase when MMF is co-administered in adults with chronic refractory gout. We have developed a decision table (see Figure 4) indicating when we will have sufficient evidence to move forward to a full scale clinical trial. Figure 4 compares the success rates in the peg+MMF arm (N=24) versus peg+PBO (N=8). The area in green is the area that we will lead us to recommend continuing to test the treatment approach in a full scale study assuming safety. This green area represents the area that achieves a significant (2 tailed p < 0.10) Fisher's exact test that peg+MMF is better than pegloticase alone. The yellow area represents an achievement of a 2-tailed p < 0.25. If the results end up in the yellow or red areas, we will examine the Ab assays to determine if there is a clear significant difference in immune response. Based on these sample sizes, the mean difference in Ab titer level needs to be at least 1 standard deviation unit apart to achieve 73% power. Nevertheless, this would be a large difference for a clinical outcome variable, but for a marker such as Ab titers this is not unreasonable. Should the titer distributions not be consistent with normality assumptions, nonparametric analyses using a Wilcoxon test will be used, since the titer levels are already measured on a log scale precluding a simple transformation to achieve normality. Participants before the 12 weeks primary endpoint that do not tolerate MMF, or are lost to follow-up, withdraw, or are otherwise not evaluable will be counted as failures but not non-responders in sensitivity analyses. MMF efficacy will be examined by the proportion of responders and tested against the control group rate using Fisher's exact test. Success rates of the efficacy primary outcome will be determined using summary statistics and 95% confidence intervals. In the event of missing antibody data, imputations will be considered to assure data completeness for our analyses using PROC MI and PROC MIANALYZE procedures with 5 replicates per value. All analyses will be conducted using SAS (V9.4, Cary, North Carolina).

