		 infusion. Removal of CBC collection at run-in visit Collection of banked specimen to measure adherence to MMF at all study visits during the dual therapy phase Supply participants with a two-week supply of MMF/placebo and assess compliance at every infusion visit during the dual therapy phase Addition of HDL/LDL collection time points Addition of gene expression and epigenetics blood collection time points 	at screening and before each infusion visit Recommendation from the DSMB By decreasing the number of pills given to participants, it will decrease participant burden due to high volume of pills and will increase compliance with study medication Not usually included on CMP, need to specifically ask for lab values on lab order sheet Tests added to measure the effect of urate-lowering therapy on the epigenome and gene expression
7.0	07/18/2018	Addition of corticosteroids as second- tier rescue medication	To improve patient quality and avoid dropouts, corticosteroids will be given if first-line medications (NSAIDS and colchicine) are ineffective
8.0	07/19/2018	Addition of medical monitors	Drs. [name] and [name] have been added as medical monitors, and will assist/provide site investigators in answering clinical relevant questions
9.0	09/13/2018	 Deletion of LDL and HDL lab collection Addition of sUA check at Visit 4 	 Lab values are not necessary To gain a better understanding of the sUA levels in between infusion 1 and 2.
10.0	12/04/2018	Revision of follow-up visits post participant treatment failure/infusion reaction. Will conduct visit 17 (two weeks post treatment failure/infusion reaction) and visits 18-20 (once a month for three months)	Participants who have experienced pegloticase treatment failure or otherwise discontinue pegloticase and are off study drug (MMF or placebo) require less regular safety evaluations. The half-life of MMF and pegloticase (the active medications) is about 17 hours and 10-12 days respectively. Adverse effects, which may be attributable to either drug, are time limited following treatment discontinuation. This revision will limit participant burden and encourage continuation in study.
11.0	1/10/2019	Addition of a weight restriction of 160kg	To minimize the likelihood of primary pegloticase treatment failures due to weight exceeding 160kg
12.0	1/13/2020	 Clarified recording of lab results and the process for signing off on labs AE/SAE review 	Request from NIAMS/KAI Request from NIAMS/KAI

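### Does the attend-every-visit protocol population bias the response comparison by dropping non-responders?

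*Combined protocol and SAP*

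**What the plan says.** Section 10.3 names two sets. The analysis population is mITT: everyone enrolled who took at least one dose of MMF or placebo. The other is the protocol population, and that "population will be all participants who attend all study visits and complete the trial". Section 5.4 ties completion to all phases of the study.

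Under Section 8.1, "participants with two consecutive serum urate levels above 6 mg/dL shall be classified as a non-responder and discontinued from the study". The samples that drive this rule are at least the pre-infusion ones: "Investigators will obtain a pre-dose serum urate sample for all patients and review results". After discontinuation, Section 8.1 says that "the participant will complete visit 17 (two weeks post discontinuation) and visits 17-20". The reminder under Visit 17 in Section 9 agrees: "if a participant is discontinued from the study, they will move into long-term follow-up and will be asked to complete visits 17", plus the three monthly visits that follow. The version 10.0 entry in Section 11.4 gives the reason: treatment failures need less frequent safety evaluation, and a shorter path limits burden.

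The Follow-up paragraph that closes the visit descriptions in Section 9 reads differently. If study drug is discontinued and consent is not withdrawn, "the subject will be followed for the full study period and all data will be collected as scheduled".

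Section 10.4.1 covers participants who do not tolerate MMF, are lost, withdraw or are otherwise not evaluable before Week 12. They "will be counted as failures but not non-responders in sensitivity analyses".

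**The concern.** A per-protocol type of set should remove people for departing from the protocol. This one can remove people for following it. A participant who takes every capsule and infusion, loses urate control and is then moved to Visit 17 as instructed has not attended every scheduled visit. The 80% pill-count criterion in Sections 7.2.1 and 7.4 is not part of the definition, so a poorly adherent responder who attends every visit stays in.

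Membership would then depend on the endpoint. A response comparison in this set could not support or contradict the mITT result: if all failures leave, both arms show complete response whatever MMF does. The set is one of only two listed, so a reader may expect a supportive analysis to be run on it.

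**Working it through.** **Inputs.** Response rates of 60% (control) and 80% (MMF): Section 10.2. Arm sizes 8 and 24, with Fisher's exact test at two-tailed p < 0.10 for the green zone: Section 10.4.1. Visit schedule: Table 1. The documents do not give the share of failures that would leave the set, so it is varied from 0 to 100%.

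**The plan's own figure.** For 60% vs 80%, 80% power, two-sided 5%, pooled variance under the null:

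n = [1.96·√(2·0.7·0.3) + 0.8416·√(0.6·0.4 + 0.8·0.2)]² / 0.2² = (1.270 + 0.532)² / 0.04 ≈ 81.2, rounded up to 82 per group, as stated in Section 10.2. The planning rates are therefore used as given.

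**Visits missed on the jump-to-Visit-17 reading.**

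| Rule first met at | Visits skipped | Number |
|---|---|---|
| Visit 5 (only if the Week 1 sample counts) | 6–16 | 11 |
| Visit 7 (Week 4, pre-infusion samples only) | 8–16 | 9 |
| Visit 11 (Week 12) | 12–16 | 5 |
| Visit 12, 13, 14, 15 | up to 16 | 4, 3, 2, 1 |
| Visit 16 | none | 0 |

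On this reading, anyone who meets the rule by Week 12 misses at least five visits.

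**Effect on a response comparison, if one were made.** Expected failures are 24 × 0.20 = 4.8 and 8 × 0.40 = 3.2, or 8 of 32. Expected responders are 19.2 and 4.8. If a share f of failures leaves each arm and no responder leaves:

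MMF rate = 19.2 / (19.2 + 4.8(1 − f)); placebo rate = 4.8 / (4.8 + 3.2(1 − f)).

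| f | MMF | Placebo | Difference (points) |
|---|---|---|---|
| 0 | 80.0% | 60.0% | 20.0 |
| 0.25 | 84.2% | 66.7% | 17.5 |
| 0.50 | 88.9% | 75.0% | 13.9 |
| 0.75 | 94.1% | 85.7% | 8.4 |
| 0.90 | 97.6% | 93.8% | 3.8 |
| 1 | 100% | 100% | 0 |

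Example: 20/24 vs 3/8 gives Fisher p = 0.023, in the green zone. With every failure removed it becomes 20/20 vs 3/3, p = 1.0.

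**How firm these figures are.** Only the last row is robust; it needs just some responders left in each arm. The others assume equal dropping and no responder missing any of 20 scheduled visits.

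- If 30% of responders in each arm also miss a visit, the f = 0.50 row becomes 13.44/15.84 = 84.8% vs 3.36/4.96 = 67.7%, a difference of 17.1 points.
- If all MMF failures leave, and placebo loses 2.0 of its 3.2 failures and half its responders, the result is 100% vs 2.4/3.6 = 66.7%, or +33.3.
- If MMF keeps all failures but loses half its responders, and all placebo failures leave, it is 9.6/14.4 = 66.7% vs 100%, or −33.3.

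Under partial dropping, neither size nor direction can be fixed from the documents.

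**Where the set is used.** Reading through Section 10.4: the Fisher test and Figure 4 (10.4.1, 10.4.2), safety, durability, antibodies and patient-reported outcomes (10.4.3), baseline tables (10.4.4) and missing data (10.4.7). None names the protocol population. The one sensitivity rule for dropouts keeps them in as failures, the opposite of a completers' analysis. The comparison of patient-reported outcomes by responder status needs non-responders present.

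**The case for a change.** The best case for acting is that a set with no assigned use can be given one after the results are known. Membership also turns on which passage the analyst follows: Section 8.1 with the Visit 17 reminder, or the Follow-up paragraph of Section 9. Deleting the set, or adding a sentence that keeps discontinued non-responders as failures, would cost little.

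The conditional statement stands: on the Visit 17 reading, a response comparison in this set is outcome-selected. The version 10.0 rationale also makes that reading the more natural one. But the exclusion is not certain. The Follow-up paragraph keeps discontinued participants on the full schedule, and attending all study visits can be read as all visits required of that participant. A single urate value above 6 mg/dL may fail the endpoint without triggering the two-value rule, so such a failure could remain in the set. Failures through intolerance or loss would ordinarily leave a per-protocol set anyway.

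Any use of the set would be an unplanned addition, reported beside the mITT result. Redefining it is also less simple than it looks. The new definition would rest on a non-response rule that Sections 3.3.1, 4 and 8.1 word differently, and on follow-up visits that Sections 8.1 and 9 describe differently. Those passages must be reconciled for trial conduct in their own right; no planned analysis on the protocol population waits on that.

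**Conclusion.** No change to the plan follows, because there is nothing to gain in any planned result. The mITT analysis, the 24-against-8 decision table and the secondary analyses are the same whether the protocol population is redefined, deleted or left alone. The size of the effect on planned output is zero.

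The collapse from 20 points to 0 describes an analysis that the plan does not contain. It assumes the Section 10.2 rates, the Visit 17 reading, and that every failure leaves while some responders remain in each arm. The intermediate figures are illustrations under assumed drop shares. Section 10.4.3 also describes primary and secondary analyses alike as descriptive, so a supportive set would carry little weight in this pilot. An analyst who did tabulate response in a protocol set would sensibly keep participants discontinued for non-response as failures, since their endpoint is fully observed.
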